#### **7.7.7. PBMC in relationship with tumor response in each cohort**

The same strategy of above (SAP section 8.7.5) will be applied for this analysis.

#### **7.8. Interim Analysis**

There will be 3 interim safety analyses in this study. After 6 and 12 patients on Cohort 1 and 6 patients on Cohort 2 complete surgery, the study will be monitored for nivolumab or nivolumab/lirilumab treatment-related toxicities as noted below.

- Any Grade hypophysitis, meningitis, or immune-related neurologic AEs
- Grade 2 or higher myocarditis
- Persistent Grade 2 immunologic AEs (such as colitis, pneumonitis, and nephritis) that do not recover to Grade 1 or resolve within 6 weeks after the last dose of study drug (Exceptions: rash, fatigue, amylase/lipase elevations, other electrolyte abnormalities).
- Grade 3 or higher immunologic AEs such as uveitis, pericarditis, hepatitis, colitis/diarrhea, nephritis, pancreatitis, myositis, endocrine, rash, etc., except Grade 3 hypothyroidism or Grade 3 infusion reaction.
- Grade 4 non immunologic AEs, as well as Grade 4 hypothyroidism or Grade 4 infusion reaction.

The first interim safety analysis will be performed as soon as the 6th patient in cohort 1 complete radical cystectomy (RC) surgery. A treatment-related AE by toxicity grade and SOC summary tables will be provided to clinical team review to determine whether 3 or more patients meet above specified AEs. If 3 or more patients are identified, the study will be suspended for a safety review.

An AE listing will also be provided for clinical team review.

The 2nd interim safety analysis will be performed as soon as the 12th patient in cohort 1 complete RC surgery. The same AE analysis as the first interim analysis will be performed for the all 12 patients. If 6 or more patients experience above specified AEs, the study will be suspended for a safety review.

The 3rd interim safety analysis will be performed as soon as the 6th patient in cohort 2 complete RC surgery. The same AE analysis will be repeated for the all 18 patients. If 9 or more patients experience above specified AEs, the study will be suspended for a safety review.

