14.1.2	Tumor Infiltrating CD8+ T-Cell Density.....	53
14.1.3	Percentage CD8+ Tumor Infiltrating T-Cell	54
14.1.4	PD-1 and PD-L1 IHC	54
14.1.5	Banking for Future Research: Additional Analysis	54
14.2	Correlative Studies: Mandatory Peripheral Blood Samples and Analysis	55
14.2.1	Peripheral Blood Assessments.....	55
14.2.2	Peripheral Blood Lymphocyte Subsets	55
14.2.3	Natural Killer Cell (NK-cell) Activation	55
14.2.4	ctDNA Analysis	55
14.2.5	Cytokine Analysis	56
14.3	Correlative Studies: Mandatory Urine Samples and Analysis	56
14.3.1	Urine Assessment and Sample Collection	56
14.3.2	Banking for Future Research: Urine Marker Analysis	56
14.4	Research Samples Processing and Shipment	56
14.4.1	FFPE Tissue Block or Slide Samples.....	56
14.4.2	Peripheral Blood Samples	56
14.4.3	Urine Sample Processing	58
15.	Administrative	59
15.1	Protocol Compliance.....	59
15.2	Institutional Review Board (IRB).....	59
15.3	Informed Consent Procedures.....	59
15.4	Safety Communication.....	60
15.5	Monitoring	60

15.6	Study Records	60
15.7	Electronic Case Report Form (eCRF) Information	61
15.8	Records Retention	61
16.	References	62
Appendix I	ECOG Performance Status	65
Appendix II:	Cockcroft-Gault Formula	66
Appendix III:	Management Algorithms for Endocrinopathy, Gastrointestinal, Hepatic, Neurological, Pulmonary, Renal, and Skin Adverse Events.....	67
Appendix IV:	RECIST Version 1.1	74
Appendix V:	Bladder Cancer TNM Staging	79
Appendix VI:	Investigator’s Statement.....	80

PrECOG STUDY SITE CONTACT

[name]
Project Manager
PrECOG, LLC
[name]
[name]
[name]
[contact]
Email: [contact]

MEDICAL MONITOR

[REDACTED]
[name]
[name]
[name]
During normal business hours
(8:30 am-5:00 pm EST):
[contact]
After normal business hours:
[contact]
Email: [REDACTED]
SAE Email: [contact]

Brief Protocol Synopsis

[figure not shown]
See Protocol Document Sections for complete details

Study Schema

Phase Ib

Key Eligibility

- Cisplatin-Ineligible or Cisplatin-Refusing Patients
- Performance Status 0-2
- Muscle Invasive Bladder Cancer (Clinical T2-T4a, N0-N1, M0)
- Sufficient Tissue for CD8+T-Cell Density Assessment

Treatment should begin within 10 working days of registration.

Accrual Goal: Maximum of 43 patients enrolled for 36 eligible, treated patients.

Cohort 1: 12 eligible, treated patients.

Cohort 2 (start enrolling after Cohort 1 completes accrual): 24 eligible, treated patients.

Number of Sites: Approximately 8 sites

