5.4 Interim Safety Analysis

After 6 and 12 patients on Cohort 1 and 6 patients on Cohort 2 complete surgery, the study will be monitored for nivolumab or nivolumab/lirilumab treatment-related toxicities as noted below.

- Any Grade hypophysitis, meningitis, or immune-related neurologic AEs

- Grade 2 or higher myocarditis
- Persistent Grade 2 immunologic AEs (such as colitis, pneumonitis, and nephritis) that do not recover to Grade 1 or resolve within 6 weeks after the last dose of study drug (Exceptions: rash, fatigue, amylase/lipase elevations, other electrolyte abnormalities).
- Grade 3 or higher immunologic AEs such as uveitis, pericarditis, hepatitis, colitis/diarrhea, nephritis, pancreatitis, myositis, endocrine, rash, etc., except Grade 3 hypothyroidism or Grade 3 infusion reaction.
- Grade 4 non immunologic AEs, as well as Grade 4 hypothyroidism or Grade 4 infusion reaction.

There will be no suspension to accrual after the first 6 patients in each cohort. Also, accrual will start on Cohort 2 once accrual to Cohort 1 is complete (unless needed based on toxicity noted).

If 3 or more of these 6 patients on a single cohort experience nivolumab or nivolumab/lirilumab treatment-related adverse events as noted above, the study will be suspended for a safety review.

6. Treatment Plan

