13.1.1 Interim Safety Analysis (Primary Endpoint)

Treatment-related toxicities as noted below related to nivolumab or nivolumab/lirilumab will be monitored in each cohort of the study separately after 6 and 12 patients in Cohort 1 and 6 patients in Cohort 2 have completed surgery. There will be no suspension to accrual.

- Any Grade hypophysitis, meningitis, or immune-related neurologic AEs
- Grade 2 or higher myocarditis
- Persistent Grade 2 immunologic AEs (such as colitis, pneumonitis, and nephritis) that do not recover to Grade 1 or resolve within 6 weeks after the last dose of study drug (Exceptions: rash, fatigue, amylase/lipase elevations, other electrolyte abnormalities).
- Grade 3 or higher immunologic AEs such as uveitis, pericarditis, hepatitis, colitis/diarrhea, nephritis, pancreatitis, myositis, endocrine, rash, etc., except for Grade 3 hypothyroidism, Grade 3 pruritus or Grade 3 infusion reaction.
- Grade 4 non immunologic AEs, as well as Grade 4 hypothyroidism or Grade 4 infusion reaction.

If 3 or more of these 6 patients on a single cohort experience treatment-related adverse events as noted above related to nivolumab or nivolumab/lirilumab, the study will be suspended for a safety review. The following table gives the probabilities of stopping given various probabilities of toxicity.

True but unknown probability of immunologic toxicity	0.17	0.25	0.33	0.42	0.5
Probability of suspension	0.06	0.17	0.32	0.49	0.66

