### **7.1. Study Design and Sample Size Considerations**

This is a Phase Ib study evaluating whether the addition of lirilumab to nivolumab is feasible and safe in patients with cisplatin-ineligible muscle-invasive urothelial carcinoma of the bladder in the neoadjuvant therapy setting. Eligible patients will be assigned sequentially to either nivolumab monotherapy in Cohort 1, and if there is no negative safety signal (assessed by interim safety analyses) after the first 12 patients, subsequent patients will be assigned to Cohort 2 treated with nivolumab/lirilumab.

There will be 12 patients in cohort 1 treated with nivolumab and 24 patients in cohort 2 treated with nivolumab+ lirilumab for the final analysis.

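### Cohort 2 has one safety look, at 6 of its 24 patients: no numerical suspension rule covers the other 18, and the SAP's pooled count makes that one look weaker still

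*SAP*

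**What the plan says.** The look schedule is the same in three places. Protocol 5.4 sets the looks "After 6 and 12 patients on Cohort 1 and 6 patients on Cohort 2 complete surgery". SAP 7.8 gives the total, "There will be 3 interim safety analyses in this study", with the same timing. Protocol 13.1.1 says that toxicities "will be monitored in each cohort of the study separately after 6 and 12 patients in Cohort 1 and 6 patients in Cohort 2"; there too, a look falls due once those patients have had their operation. Accrual is not paused for the looks ("There will be no suspension to accrual").

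The cohort sizes are also consistent: "There will be 12 patients in cohort 1 treated with nivolumab and 24 patients in cohort 2 treated with nivolumab+ lirilumab" (SAP 7.1). The protocol's Study Schema has Cohort 2 open once Cohort 1 is full: "Cohort 2 (start enrolling after Cohort 1 completes accrual): 24 eligible, treated patients".

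The suspension thresholds are not the same:

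- Protocol 5.4 and 13.1.1 give one threshold, applied within a cohort: "If 3 or more of these 6 patients on a single cohort experience treatment-related adverse events" of the listed kinds, the study is suspended for a safety review. The protocol gives no separate count for the 12-patient look.
- SAP 7.8 uses 3 of 6 and then 6 of 12 in Cohort 1. At the Cohort 2 look it pools all 18 patients from both cohorts and suspends at 9 or more.

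SAP 2.1 says that the SAP supersedes the protocol's statistical considerations, while SAP section 8 says that no changes from the protocol are planned. A data safety monitoring board appears in both abbreviation lists, but neither document gives it a role.

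**The concern.** Protocol 13.1 states the study question as whether adding lirilumab to nivolumab is feasible and safe, and safety is the primary objective. The cohort that answers this question has its only count-based check after a quarter of its patients (6 of 24). Once that look is passed, no number of listed toxicities among patients 7 to 24 triggers suspension under protocol 5.4, protocol 13.1.1 or SAP 7.8.

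A 6-patient look often misses a high rate, and the pooled version in the SAP misses it far more often, because Cohort 1 results dilute those of Cohort 2. The patients are awaiting potentially curative surgery, and losing cystectomy to treatment-related toxicity is itself a secondary endpoint. Late recognition of a high rate therefore has a cost to patients.

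**Working it through.** **Inputs.** Looks, thresholds and the table of suspension probabilities: protocol 13.1.1 and SAP 7.8. Cohort sizes of 12 and 24: SAP 7.1. Accrual of 2-3 patients per month: protocol 5.1. Up to 10 working days from registration to first dose: protocol 4.3. Doses at weeks 0 and 4, then surgery within 6 weeks: protocol section 5.

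**1. Reproduce the protocol's table.** For X ~ Bin(6, p), the suspension probability is P(X ≥ 3). With p = 1/6, 1/4, 1/3, 5/12 and 1/2 this gives 0.062, 0.169, 0.320, 0.490 and 0.656. The protocol prints 0.06, 0.17, 0.32, 0.49 and 0.66, so the table describes a single 3-of-6 look. At the printed rates 0.17, 0.33 and 0.42 the values are 0.066, 0.313 and 0.497. The printed rates are used below.

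**2. Chance that Cohort 2 passes under the protocol's rule.** At 0.50: 1 − 0.656 = 0.344. At 0.42: 1 − 0.497 = 0.503. After that, no count applies to 18 of 24 patients (75%).

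**3. The same look under the SAP's pooled rule.** Let X₁ ~ Bin(12, p₁) for Cohort 1 and X₂ ~ Bin(6, p₂) for Cohort 2. The suspension probability is Σᵢ P(X₁ = i) · P(X₂ ≥ 9 − i). Assume p₁ = 0.17 and p₂ = 0.50:

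- i ≤ 2 (probability 0.666): suspension is impossible, because 2 + 6 = 8 < 9
- i = 3: 0.2021 × 0.0156 = 0.0032
- i = 4: 0.0931 × 0.1094 = 0.0102
- i = 5: 0.0305 × 0.3438 = 0.0105
- i = 6: 0.0073 × 0.6563 = 0.0048
- i ≥ 7: about 0.0013

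The total is 0.030, against 0.656 under 3 of 6. If Cohort 1 has passed its own SAP looks it has at most 5 events, so the pooled rule then needs at least 4 of 6 in Cohort 2. In that case it is always the weaker rule.

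**4. Add a Cohort 2 look at 12 with the SAP's 6-of-12 count.** With Y ~ Bin(6, p) for patients 7 to 12, the cumulative probability is P(X ≥ 3) + Σ P(X = x) · P(Y ≥ 6 − x), summed over x = 0, 1, 2. At p = 0.50 the added part is 0.0156 × 0.0156 + 0.0938 × 0.1094 + 0.2344 × 0.3438 = 0.0911, so the total is 0.6562 + 0.0911 = 0.747.

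| True rate | 3/6 only | 3/6 and 6/12 | Gain |
|---|---|---|---|
| 0.17 | 0.066 | 0.068 | 0.002 |
| 0.25 | 0.169 | 0.182 | 0.013 |
| 0.42 | 0.497 | 0.568 | 0.071 |
| 0.50 | 0.656 | 0.747 | 0.091 |

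**5. Who could still benefit.** The longest interval from registration to surgery is 2 + 4 + 6 = 12 weeks, about 2.8 months. At 2-3 registrations per month, 5.5 to 8.3 further patients register in that time. When the 12th patient has surgery, about 17.5 to 20.3 are registered, leaving about 4 to 7 of 24. When the 18th has surgery, 18 + 5.5 = 23.5 or more are registered, which is essentially the whole cohort.

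**The case against.** The best defence is that one early look is an acceptable choice for a small Phase Ib study, and that both documents state the schedule consistently. Four points support it.

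- **Other safeguards cover all 24 patients.** These are serious adverse event reports within 24 hours and expedited regulatory reporting (protocol 9.3), patient-level discontinuation rules (section 7), and closure of the study by the sponsor (8.3). This stands. A reader might infer that patients 7 to 24 are unmonitored, and the documents do not support that. What is missing is a rule that adds up events in the cohort and requires a review at a stated count.
- **The high rates may be unlikely.** Protocol 1.6 reports grade 3-4 treatment-related events in 15% (24/159) on the combination. That category differs from the listed toxicities, but it is the only combination benchmark given. At 0.17 the extra look adds 0.002. This limits the expected benefit. The protocol's own table, however, runs up to 0.50, and a suspension rule exists for the case where the expected rate is wrong.
- **Cohort 1 is not really protected twice.** A reader might contrast 12 of 12 patients monitored with 6 of 24. But by the 12th Cohort 1 surgery all Cohort 1 patients have been treated, so that look can act only on Cohort 2 enrolment, and the protocol gives it no count of its own. Each cohort has one look that can spare its own patients.
- **The gain in patients is small.** At true rates of 0.42 to 0.50, a gain of 0.071 to 0.091 times about 4 to 7 unregistered patients is roughly 0.3 to 0.6 patients in expectation, and less if accrual is faster. This stands too.

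A reader might also credit a further look at 18 (9 or more), which takes the probability at 0.50 to 0.791. By then nearly all 24 patients are registered, so it could affect only those awaiting a second dose or surgery.

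**Conclusion.** The point holds, with a limited scope. Cohort 2 has one cohort-level look at 6 of 24 patients, and no numerical suspension rule applies afterwards. Under the protocol's rule that look misses a true rate of 0.50 about one time in three, and a rate of 0.42 about half the time. Under the SAP's pooled rule it hardly functions: suspension probability is about 0.03 at the assumed rates of 0.17 and 0.50. The pooled count also contradicts the protocol's instruction to monitor each cohort separately, and SAP section 8 does not declare the change.

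A Cohort 2 look at 12 adds 0.07 to 0.09 to the suspension probability at rates of 0.42 to 0.50, and little at low rates. These figures assume independent patients with a constant toxicity rate. The count of patients still to be registered assumes 2-3 registrations per month and the longest permitted interval to surgery. Protocol 6.1 already describes infusion reactions in Cohort 2, so the practical gain shrinks with each patient entered before an amendment takes effect.

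**What to change.** 1. Reconcile SAP 7.8 with protocol 5.4 and 13.1.1 so that the Cohort 2 look counts Cohort 2 patients only. Remove the pooled 9-of-18 rule rather than leaving it beside a cohort-specific one.
2. In all three sections, add a Cohort 2-only look when 12 Cohort 2 patients have completed surgery, with suspension for safety review at 6 or more of 12. Base the trigger on completed surgery, as the existing looks do, because one listed toxicity cannot be classified until 6 weeks after the last dose.
3. Extend the table in protocol 13.1.1 to show the cumulative suspension probabilities for the two looks.

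A look at 18 is optional.

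The cost is one more run of the existing interim tables and listing and a short amendment to both documents. The false-suspension probability rises by about 0.002 at a true rate of 0.17 and by about 0.013 at 0.25.

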13.1 Study Design & Sample Size Considerations

This is a Phase Ib study evaluating whether the addition of lirilumab to nivolumab is feasible and safe in patients that are either cisplatin-ineligible or refuse cisplatin-based chemotherapy and have muscle-invasive urothelial carcinoma of the bladder in the neoadjuvant therapy setting. Eligible patients will be assigned sequentially to either nivolumab monotherapy in Cohort 1, and if there is no negative safety signal (see next paragraph) after the first 12 patients, subsequent patients will be assigned to Cohort 2 treated with nivolumab/lirilumab.

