## **2. INTRODUCTION**

### **2.1. Objective of the Statistical Analysis Plan**

This statistical analysis plan (SAP) describes the planned analysis of the safety and efficacy data from this study. A detailed description of the planned tables, figures and listings (TFLs) to be presented in the Clinical Study Report (CSR) is provided in the accompanying TFL template document.

The intent of this document is to provide guidance for the analysis of data related to safety and efficacy to describe any applicable statistical procedures. In general, the analyses come directly from the protocol, unless they have been modified by agreement between the Sponsor and Quality Data Services, Inc. (QDS). A limited amount of information concerning this study (e.g., objectives, study design) is summarized to help the reader interpret the accompanying TFL templates. That information is not a synopsis of the study and does not require review or approval because it is simply extracted from the protocol. Attached signatures indicate approval of the statistical analysis sections of the SAP, as well as accompanying TFL templates. These sections must be agreed upon prior to database lock. When the SAP and TFL templates are agreed upon and finalized, they will serve as the template for a portion of this study's CSR.

This SAP supersedes the statistical considerations identified in the protocol; where considerations are substantially different, they will be so identified. If additional analyses are required to supplement the planned analyses described in this SAP, they may be performed and will be identified in the appropriate section of the CSR. Any substantial deviations from this SAP will be agreed upon between the sponsor and QDS. Deviations from this SAP, both substantial and non-substantial, will be documented in the CSR. Any updates to their respective analyses, study designs, and TFL presentations after this SAP is finalized and approved will be documented in a running Note to the SAP document.

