### **7.2. Methodology**

Continuous data will be summarized with the following descriptive statistics: number of observations (n), mean, standard deviation (SD), median, minimum (min), and maximum (max). Categorical data will be summarized with frequencies and percentages. Hypothesis testing for categorical data will use nonparametric methods.

In general, listings will be presented by patient. Tables will be summarized and presented by cohort in specific analysis populations.

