## **8. SUMMARY OF CHANGES FROM PROTOCOL-SPECIFIED ANALYSES**

No changes are planned.

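### The third safety look in SAP 7.8 pools both cohorts (9 of 18), contradicts the protocol's separate 3-of-6 rule for Cohort 2, and is not declared as a change

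*SAP*

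**What the plan says.** Protocol 13.1.1 says the listed toxicities "will be monitored in each cohort of the study separately after 6 and 12 patients in Cohort 1 and 6 patients in Cohort 2"; each look is timed by surgery. Its trigger for suspension and safety review is: "If 3 or more of these 6 patients on a single cohort experience treatment-related adverse events as noted above". Protocol 5.4 has the same threshold: "If 3 or more of these 6 patients on a single cohort experience nivolumab or nivolumab/lirilumab treatment-related adverse events as noted above". Section 13.1.1 also tabulates suspension probabilities of 0.06, 0.17, 0.32, 0.49 and 0.66 for true toxicity rates of 0.17, 0.25, 0.33, 0.42 and 0.5.

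SAP 7.8 keeps the three-look schedule. Look 1 suspends at 3 or more of the first 6 Cohort 1 patients, and look 2 at 6 or more of the 12 Cohort 1 patients. Look 3 is timed by the sixth Cohort 2 cystectomy: "The same AE analysis will be repeated for the all 18 patients. If 9 or more patients experience above specified AEs", the study is suspended. No Cohort 2 criterion is given for that look.

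On precedence, SAP 2.1 says: "This SAP supersedes the statistical considerations identified in the protocol; where considerations are substantially different, they will be so identified". SAP 8, which lists changes from the protocol's analyses, says: "No changes are planned".

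**The concern.** Protocol 13.1 describes the study as "evaluating whether the addition of lirilumab to nivolumab is feasible and safe". The look after six Cohort 2 surgeries is the only scheduled interim check on the combination. Pooling dilutes those six patients with twice as many who never received lirilumab. The better nivolumab alone is tolerated, the harder it becomes for the rule to react to a toxic combination.

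Keeping the 50% fraction (3/6, 6/12, 9/18) does not make the rules equivalent, because 9 of 18 asks about the average of two different regimens. Accrual is not held for the look, and up to 24 − 6 = 18 further patients are due in Cohort 2. A missed trigger therefore matters for patients still to be treated. The protocol's table of suspension probabilities describes look 1 of the SAP but not look 3.

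**Working it through.** **Inputs.** From the documents: 12 patients in Cohort 1; 6 in Cohort 2 at look 3; the protocol threshold of 3 of 6; SAP thresholds of 3 of 6, 6 of 12 and 9 of 18. Assumed, because the documents give no Cohort 1 rate for this event set: p1 = 0.10, 0.167, 0.25, 0.333. The Cohort 2 rate p2 is set to 0.50 (the top of the protocol's table) and to 0.67 (beyond it).

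**Step 1: reproduce the protocol's table.** P(X ≥ 3), X ~ Bin(6, p), at p = 1/6, 1/4, 1/3, 5/12, 1/2 gives 0.062, 0.169, 0.320, 0.490, 0.656. Rounded, these are the printed values, so the table belongs to the single-cohort 3-of-6 rule.

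**Step 2: what 9 of 18 requires of Cohort 2.** With X1 events in Cohort 1, look 3 needs X2 ≥ 9 − X1. No rate is assumed here.

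| Cohort 1 events | Cohort 2 events needed, of 6 |
|---|---|
| 0, 1, 2 | 9, 8, 7: impossible |
| 3 | 6 |
| 4 | 5 |
| 5 | 4 |
| 6 | 3 |

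A Cohort 1 that passed look 2 has at most 5 events. Exactly 3 of 6 in Cohort 2, which triggers the protocol rule, then cannot trigger the SAP rule. It suffices only with 6 or more Cohort 1 events, for example if the study resumed after a review.

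**Step 3: suspension probabilities.** Cohort 1 is two blocks of 6 at rate p1. *Passed* means fewer than 3 events in the first 6 and fewer than 6 in all 12. The pooled rule suspends with probability Σ P(X1 = k) × P(X2 ≥ 9 − k).

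Example, p1 = 0.25 and p2 = 0.50. Given a pass, P(X1 = 3, 4, 5) = 0.2869, 0.1722, 0.0631. The Cohort 2 tails P(X2 ≥ 6, 5, 4) are 0.0156, 0.1094, 0.3438. The sum is 0.2869 × 0.0156 + 0.1722 × 0.1094 + 0.0631 × 0.3438 = 0.0045 + 0.0188 + 0.0217 = 0.045, against 0.656 for 3 of 6.

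| Quantity | p1 = 0.10 | 0.167 | 0.25 | 0.333 |
|---|---|---|---|---|
| Pooled suspension, p2 = 0.50, passed | 0.004 | 0.016 | 0.045 | 0.085 |
| Same, unconditional | 0.005 | 0.028 | 0.10 | 0.23 |
| Pooled suspension, p2 = 0.67, passed | 0.014 | 0.052 | 0.13 | 0.23 |
| Same, unconditional | 0.018 | 0.076 | 0.21 | 0.40 |
| 9 of 18 unreachable (X1 ≤ 2), passed | 90% | 72% | 48% | 28% |
| Same, unconditional | 89% | 68% | 39% | 18% |
| SAP rule silent when X2 ≥ 3, p2 = 0.50, passed | 99% | 98% | 93% | 87% |
| Same, unconditional | 99% | 96% | 85% | 68% |

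The 3-of-6 rule gives 0.66 at p2 = 0.50 and 0.90 at p2 = 0.67.

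**Step 4: equal rates in both cohorts.** P(X ≥ 9), X ~ Bin(18, p), at the printed rates 0.17, 0.25, 0.33, 0.42, 0.5 is 0.001, 0.019, 0.10, 0.32, 0.59, without conditioning on the earlier looks. The two rules come close only when nivolumab alone is itself toxic in about half of patients.

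**The case against.** The strongest reply is that the protocol rule may still govern. SAP 2.1 supersedes only the protocol's statistical considerations. The 3-of-6 rule also stands in protocol 5.4, under study design, and protocol 15.1 requires conduct as the protocol describes. On that reading 3 of 6 in Cohort 2 would still suspend the study, and the figures above describe SAP 7.8 taken alone. This is a fair limit on the probabilities. It does not remove the conflict: SAP 7.8 says that the study will be suspended at 9 of 18, and two rules then exist for one look.

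Other points:

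- *The 18 patients may be meant only as cumulative reporting.* The suspension sentence attaches to those 18, and no other threshold is stated.
- *Cohort 2 counts will be visible.* SAP 7.2 says "Tables will be summarized and presented by cohort in specific analysis populations", the clinical team receives an adverse event listing, and serious events are reported within 24 hours. All true, but none is a decision rule for Cohort 2.
- *The protocol gives no threshold for its own 12-patient look.* Correct. The SAP's 6 of 12 fills a gap and is not criticised here. The *passed* figures depend on it, so unconditional ones are shown beside them.
- *The chosen Cohort 2 rates are high.* At 0.25 the protocol rule itself suspends only 17% of the time, so at most 0.17 can be lost.
- *The SAP may lag the protocol.* Its history aligns it to protocol V3.0 of 10 December 2019, and it differs from the supplied protocol elsewhere, for example in the TURBT window (8 against 10 weeks). V3.0's interim wording cannot be seen. Lag might explain the mismatch, but the current documents still disagree.
- *The consequence is a review, not termination, and the final by-cohort analysis is unaffected.* This bounds the harm without making the rule workable.

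**Conclusion.** The concern holds. SAP 7.8 and protocol 13.1.1 and 5.4 give incompatible suspension rules for the same look, and the SAP does not declare the difference. The structural failure needs no assumed rate: with 2 or fewer Cohort 1 events the SAP rule cannot fire whatever happens in Cohort 2, and after a Cohort 1 that passed the SAP's 12-patient look it needs at least 4 of 6 rather than 3.

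The size of the loss depends on the assumed rates, on independent binomial counts, and on SAP 7.8 being applied as written. Within those limits, the drop from 0.66 at a Cohort 2 rate of 0.50 is large over the whole range of Cohort 1 rates considered, with or without conditioning. It must be fixed, because safety is the primary objective and this is the combination's only scheduled interim look.

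**What to change.** Reconcile SAP 7.8 with protocol 13.1.1 and 5.4 so that the third look evaluates the 6 Cohort 2 patients on their own under the protocol's existing single-cohort rule, to which the published suspension probabilities apply. Keep the 18-patient table as descriptive only. Correct SAP 8 so that any remaining difference from the protocol's monitoring plan is declared, including the 6-of-12 threshold that the protocol does not contain.

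Two smaller clarifications can go into the same revision but are not part of the required change:

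- State whether treated patients who do not reach surgery count among the six. Completion of surgery may only set the timing of the look, and the SAP 7.5.1 safety population includes all treated patients.
- Reconcile the Grade 3 pruritus exception, which appears in protocol 13.1.1 but not in protocol 5.4 or SAP 7.8.

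The main change costs only wording in SAP 7.8 and 8, with no new data and no extra patients.

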## 4. STUDY DESIGN

### 4.1. General Study Design and Plan

This is a Phase Ib open-label clinical trial for patients with cisplatin-ineligible MIBC (T2-T4a, N0-N1, M0). Patients will be sequentially enrolled first into Cohort 1 treated with nivolumab alone (N=12). In the absence of the occurrence of high rate of treatment related AEs as defined in protocol Section 5.4 and 13.1.1 with neoadjuvant nivolumab treatment, the study will proceed with enrollment into Cohort 2 of neoadjuvant treatment with combination nivolumab/lirilumab. (In both cohorts, neoadjuvant treatment must start within 8 weeks of transurethral resection of the first TURBT that showed muscularis propria invasion). Each group will receive a total of 4 weeks (week 0 and 4) of neoadjuvant therapy followed by radical cystectomy (RC) with bilateral (standard or extended) pelvic lymph node dissection (PLND).

The RC with bilateral (standard or extended) PLND will occur as soon as possible but within 6 weeks after the last neoadjuvant dose in either cohort.

Off treatment visit will occur approximately 30 days following cystectomy (cystectomy is not performed, Off Treatment visit should be performed at next scheduled appointment or treating physician discretion, as clinically indicated) and patients will be followed for 100 days after neoadjuvant treatment for AEs. Adverse events may be reviewed at the next visit  $\geq$  100 days after last dose of neoadjuvant therapy or phone follow-up may be done to review adverse events.

Patients will be followed clinically and radiographically for at least 2 years post-cystectomy or when study-wide follow-up ends per standard of care. Date of diagnosis for recurrence, first subsequent therapy and survival shall be reported. Phone follow-up may also be done for patients unable or unwilling to return for follow-up evaluations.

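### At the Cohort 2 safety look the SAP suspends at 9 of 18 patients pooled over both cohorts, where the protocol suspends at 3 of 6 on a single cohort, and the SAP declares no change

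*SAP*

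**What the plan says.** **Protocol.** Section 5.4 sets the looks: "After 6 and 12 patients on Cohort 1 and 6 patients on Cohort 2 complete surgery, the study will be monitored" for five listed kinds of treatment-related toxicity. The trigger for a suspension is "If 3 or more of these 6 patients on a single cohort experience" such an event. Section 13.1.1 repeats the trigger, says that the cohorts are monitored separately, and tabulates the probability of suspension against the true toxicity rate.

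**SAP 7.8.** The first look uses 3 or more of 6 in Cohort 1. The second covers all 12 Cohort 1 patients: "If 6 or more patients experience above specified AEs", the study is suspended. The third look comes when the sixth Cohort 2 patient completes cystectomy: "The same AE analysis will be repeated for the all 18 patients". Its limit is "If 9 or more patients experience above specified AEs, the study will be suspended for a safety review".

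**Precedence.** SAP 2.1 says: "This SAP supersedes the statistical considerations identified in the protocol; where considerations are substantially different, they will be so identified". SAP 8, where a difference would be listed, says "No changes are planned". SAP 4.1 sends the reader back to the protocol for the high toxicity rate that would keep Cohort 2 from opening, "as defined in protocol Section 5.4 and 13.1.1".

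**The concern.** Protocol 13.1 puts the trial's question as whether adding lirilumab to nivolumab is feasible and safe, in patients treated before curative-intent surgery. The Cohort 2 look is the only one with a numeric limit that bears on the combination. Two-thirds of the patients in the SAP's count (12 of 18) had nivolumab alone. A well-tolerated Cohort 1 therefore dilutes a toxic Cohort 2, and the better Cohort 1 did, the harder the limit is to reach.

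The two rules also give different answers on the same data, and nothing in the SAP tells the team holding the look that they differ.

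**Working it through.** **Inputs**
- Protocol rule: 3 or more of 6, one cohort (5.4, 13.1.1).
- SAP third-look rule: 9 or more of 18, made up of 12 from Cohort 1 and 6 from Cohort 2 (7.8).
- SAP Cohort 1 limits: 3 of the first 6, then 6 of 12 (7.8).
- Cohort 1 toxicity rate p1: an assumption, because the documents give no rate for this composite. The base case is 1/6, with a range of 0.10 to 0.33. For orientation only, Protocol 1.6 cites a 15% grade 3-4 treatment-related rate (24/159) for the combination elsewhere, which is a related but different measure.

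**Step 1. Reproduce the protocol's table.** With X ~ Bin(6, p), P(suspend) = P(X ≥ 3) = 1 − [P(0) + P(1) + P(2)]. At p = 1/2 this is 1 − (1 + 6 + 15)/64 = 42/64 = 0.656. At p = 1/6, 1/4, 1/3, 5/12 and 1/2 it gives 0.062, 0.169, 0.320, 0.490 and 0.656, which round to the printed 0.06, 0.17, 0.32, 0.49 and 0.66. The table describes 3 of 6 in one cohort.

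**Step 2. Which counts can reach 9?** The Cohort 2 count needed is 9 minus the Cohort 1 count.

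| Cohort 1 count at the third look | Cohort 2 count needed |
|---|---|
| 5 | 4 of 6 |
| 4 | 5 of 6 |
| 3 | 6 of 6 |
| 2 or fewer | 7 or more, impossible |

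So with 5 or fewer in Cohort 1, the protocol's own trigger of 3 in Cohort 2 gives at most 5 + 3 = 8. The chance that Cohort 1 has 2 or fewer of 12 is 0.74 at p1 = 0.15 and 0.67 at p1 = 0.17.

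**Step 3. Suspension probability under the SAP rule.** With X1 ~ Bin(12, p1) and X2 ~ Bin(6, p2), P(suspend) = Σ P(X1 = a) · P(X2 ≥ 9 − a). Worked at p1 = 1/6, p2 = 1/2:
- a = 3: 0.1974 × 0.0156 = 0.0031
- a = 4: 0.0888 × 0.1094 = 0.0097
- a = 5: 0.0284 × 0.3438 = 0.0098
- a = 6 or more: 0.0055
- total: 0.0281

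The conditional column below restricts to a Cohort 1 that passed both its looks: at most 2 of the first 6 and at most 5 of 12. At p1 = 1/6 that has probability 0.936.

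| Cohort 2 toxicity | Protocol, 3 of 6 | SAP, 9 of 18 | SAP, given Cohort 1 passed |
|---|---|---|---|
| 1/6 | 0.06 | 0.001 | 0.0002 |
| 1/4 | 0.17 | 0.003 | 0.001 |
| 1/3 | 0.32 | 0.008 | 0.003 |
| 5/12 | 0.49 | 0.015 | 0.007 |
| 1/2 | 0.66 | 0.028 | 0.016 |

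**Step 4. Sensitivity to the assumed Cohort 1 rate**, at Cohort 2 toxicity 0.50, where the protocol rule gives 0.66:

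| p1 | SAP, 9 of 18 | SAP, given Cohort 1 passed |
|---|---|---|
| 0.10 | 0.005 | 0.004 |
| 0.17 | 0.030 | 0.017 |
| 0.25 | 0.100 | 0.045 |
| 0.33 | 0.223 | 0.084 |

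Even when a third of Cohort 1 is assumed toxic, the pooled rule suspends about a third as often as the protocol's (0.223/0.656 = 0.34).

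**The case against.** **The protocol may govern.** The SAP supersedes only the protocol's statistical considerations. Section 13.1.1 lies in that part, but 5.4 lies under Study Design. Protocol 15.1 requires the study to be run as the protocol describes, SAP 4.1 points back to 5.4, and SAP 8 disclaims any change. This stands. A reader might infer that the Cohort 2 stop has been abolished, and the documents do not support that. The loss arises only if SAP 7.8 is followed. What remains is that two live texts disagree on when to suspend.

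**The SAP keeps the same proportion.** All three limits, 3/6, 6/12 and 9/18, are one half. With a common toxicity rate of 0.50 in both cohorts, 9 of 18 would suspend with probability 0.59, not far from 0.66. But that supposes lirilumab adds no toxicity, which is what the look is there to test. At a common rate of 0.33 it already falls to 0.10 against 0.31.

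**The team would see the data.** SAP 7.8 supplies AE tables and a listing, and SAP 7.2 presents tables by cohort. A count of 3 of 6 in Cohort 2 would be visible, but SAP 7.8 attaches no action to it.

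**The Cohort 1 count is not frozen.** Persistent Grade 2 events mature 6 weeks after the last dose, AEs are followed for 100 days, and a suspended Cohort 1 could resume after review. So it is too strong to say that 3 of 6 can never trip the rule once Cohort 1 has passed its looks. The statement holds for the Cohort 1 count as it stands at the third look.

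**Timing is a separate matter.** A reader might also infer that waiting for the sixth cystectomy with accrual open is an error. It is an explicit choice in 5.4 and 13.1.1. Whether patients who miss cystectomy drop out of the six is only one reading of the text. Neither belongs to this point.

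**Conclusion.** SAP 7.8 is wrong as written for the third look. It replaces a single-cohort rule with a pooled one, against Protocol 5.4 and 13.1.1 and without the declaration that SAP 2.1 promises. The SAP's document history describes its last version as an update for consistency with the protocol, so nothing marks this as a deliberate change.

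If 7.8 is followed, the probability of suspending a combination cohort with 50% toxicity falls from 0.66 to between 0.005 and 0.22 for Cohort 1 toxicity of 0.10 to 0.33. These probabilities are unconditional. Given that Cohort 1 passed its looks they are lower still. They rest on independent patients and on the assumed Cohort 1 rate. The reachability result in Step 2 needs neither assumption. If 5.4 is held to govern, the harm is avoided, but 3 of 6 in Cohort 2 with 5 or fewer in Cohort 1 is a suspension under one document and not under the other.

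**What to change.** In SAP 7.8, replace the pooled third-look rule with: 'The third interim analysis uses the 6 Cohort 2 patients only. If 3 or more of these 6 have a listed treatment-related AE, the study is suspended for a safety review.' AE tables for all 18 patients can still be supplied as background.

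If the look has already taken place, re-read it at 3 of 6. The note in Protocol 6.1 shows that Cohort 2 dosing had begun, but the documents do not say whether the look has been held.

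The cost is two SAP sentences and at most one re-reading of data on six patients. No protocol amendment and no extra patients are needed. There will be more suspensions than under 9 of 18, but only at the rates the protocol already tabulates, including 0.06 at a toxicity rate of 0.17.
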